7.6 Reporting of Events to Sponsor

The following events should also be reported to the Sponsor within 24 hours of knowledge of the event:

- An overdose of SL-172154 or MIRV
- Suspected transmission of an infectious agent due to contamination of drug product
- Other events related to misuse of SL-172154 or MIRV

7.7 Study Halting Rules

Administration of SL-172154 will be halted if a fatal SAE related to SL-172154 is reported to the Sponsor. The Sponsor will inform the investigators immediately if such an event is reported. Screening and new study enrollment will be stopped. The Sponsor will convene an ad hoc meeting of the SMC to review the SAE and overall safety profile and provide recommendations. The study Sponsor will inform the regulatory authorities (i.e., FDA, European Medicines Agency (EMA), Health Canada, etc.) of the temporary halt and the disposition of the study.

7.8 Safety Oversight

An SMC will be implemented in this study and will consist of investigators and Sponsor representatives. Study progress and safety data will be reviewed by the SMC throughout the conduct of the study. During the study while subjects are receiving treatment with SL-172154 +MIRV or PLD, SMC meetings will be held to review relevant data with the investigators or designees during both dose escalation and dose expansion. These meetings will be held once a month (or more frequently if required) during dose escalation to share safety data and communicate results of ongoing analyses provided subjects have been enrolled and data are available to be reviewed. The SMC will operate in accordance with the SMC charter which will define roles and accountabilities as well as the process for safety review and meeting frequency. As dose escalation proceeds, the SMC will take into account data from Study SL03-OHD-105 as well as other knowledge obtained for SL-172154, including the data from the monotherapy SL-172154 dose escalation in Study SL03-OHD-101. Safety and PK data from Study SL03-OHD-101 will be shared with the SMC for SL03-OHD-105. Doses explored in SL03-OHD-105 will not exceed the highest dose cleared for safety in SL03-OHD-101. All dose escalation or safety decisions made by the SMC will be documented in writing with copies maintained at each site and in the Trial Master File at the Contract Research Organization. Based on the severity of the DLTs, indicators of potential anti-tumor activity, and other factors, a recommendation on whether to modify the dose and/or study design or continue enrollment will be made by the Sponsor collaboratively with input from the SMC. Regulatory authorities and IRBs/IECs will be notified of any decisions to prematurely halt the study or subject enrollment. See Section 14.1 for details on safety meetings.

8. ANTI-TUMOR ACTIVITY ASSESSMENTS

Although the clinical benefit of SL-172154 has not yet been established, the intent of offering SL-172154 is to provide a possible therapeutic benefit, and thus the subject will be carefully monitored for tumor response and symptom relief in addition to safety and tolerability. For the purposes of this study, subjects should be evaluated for response as outlined in the SOA. All subjects who underwent the first post-baseline disease assessment at the 8-week (PLD Cohort) or

6-week (MIRV Cohort) time point or progress or die before the first post-baseline disease assessment will be considered evaluable for response.

Refer to the SOA (Section 6.1 and Section 6.2) and Section 6.11 for the schedule of disease assessments. More frequent disease assessments may be performed at the discretion of the investigator as clinically indicated. CA-125 levels should be measured concurrently with radiologic tumor assessments (Section 6.5.9.3) and reported in EDC however response determination will be solely based on radiologic assessment in this study.

8.1 Disease Assessment

Imaging studies, preferably by contrasted computed tomography scan, for disease assessment of chest, abdomen and pelvis and all other sites of known disease will be performed at baseline and at the following intervals until disease progression as described in Section 6.11.

PET-CT, MRI, and/or bone scan should be performed as clinically indicated. The same imaging modality used at baseline should be employed subsequently. All post-baseline assessments require imaging of disease sites identified by baseline scans. Confirmatory scans should be performed at least 4 weeks (> 28 days) after initial documentation of an objective response. Contrast enhanced imaging is required unless the subject is precluded from receiving contrast (e.g., hypersensitivity, renal impairment).

If study treatment is withdrawn for reasons other than disease progression, radiographic disease assessments should continue as per the SOA until documented disease progression, the start of new anti-cancer therapy, withdrawal of consent or death.

8.1.1 Assessment of Response

Investigator-assessed response will be evaluated in this study using RECIST v1.1 [Eisenhauer, 2009]. The RECIST v1.1 guideline is included in this document (Appendix Section 16.5).

8.2 Criteria for Treatment Beyond Initial Progression

Subjects will be permitted to continue study treatment beyond initial progressive disease provided the subject does not have clinical symptoms of progression, is tolerating study treatment, has experienced no decline in their ECOG performance status and is gaining clinical benefit as assessed by the investigator. The subject must be made aware of the potential benefits and risks of continuing the study treatment in the setting of progressive disease by signing a separate written informed consent.

The subject may continue to be treated beyond disease progression until one of the following criteria is met:

- Develops clinical symptoms or signs such that the benefit-risk ratio of continuing therapy is no longer justified.
- Experiences rapid progressive disease with risk to vital organs or critical anatomical sites requiring urgent medical intervention.

9. STATISTICAL CONSIDERATIONS AND DATA ANALYSIS

9.1 Study Design and Sample Size Determinations

9.1.1 Dose Escalation

The SL-172154 dose escalation will utilize an mTPI-2 design [Guo, 2017] with a target DLT rate of 30% for the MTD.

The mTPI-2 design employs a simple Beta-Binomial Bayesian model with decision rules based on the unit probability mass from the posterior probability of DLT rate. With the target DLT rate of 30%, the posterior probability of DLT rate unit interval (0, 1) is divided into subintervals with equal length of 0.1 that correspond to different dose escalation decisions: subinterval of (0.25, 0.35) is to stay at the current dose, subintervals below 0.25 is to escalate to next higher dose, and subinterval above 0.35 is to de-escalate to the next lower dose. Subjects will be enrolled in cohorts of approximately 3 subjects during the dose escalation. After each cohort of approximately 3 subjects, the posterior unit probability for subintervals will be calculated based on a noninformative prior distribution for the DLT rate (Beta (1,1)) and the total number of subjects with DLTs and DLT-evaluable subjects for the current dose. A dose escalation/stay/de-escalation decision that corresponds to the subinterval with the highest unit probability mass will be selected. A minimum of 3 DLT-evaluable subjects will be enrolled to a dose level and evaluated for DLT before a dose escalation/stay/de-escalation decision can be made unless unacceptable toxicity is observed prior to the enrollment of 3 subjects e.g., two subjects experience DLT before the third subject enrolls. A dose level will be considered unsafe, with unacceptable toxicity and no additional subjects enrolled at that dose level and above, if it has an estimated 95% or more probability of exceeding the target DLT rate of 30%. The maximum number of subjects evaluated for DLT for each dose level will be 12 subjects (about 4 cohorts of 3 subjects) if the dose escalation decision is to stay at the current dose from the first 3 cohorts. Based on the above design, the dose escalation decision rules for each dose level are:

- Dose escalate if the observed DLT rate < 25%;
- Stay at the current dose if the observed DLT rate between 25%-33%;
- Dose de-escalate if the observed DLT rate > 33%;

See [Table 12](#) for dose escalation decision rules based on the total number of subjects evaluable for DLT and the number of DLTs observed.

Table 12 SL-172154 Dose Escalation Decision Rules for Each Dose Level Based on mTPI-2

Number of DLTs	Number of Subjects									
	3	4	5	6	7	8	9	10	11	12
0	E	E	E	E	E	E	E	E	E	E
1	S	S	E	E	E	E	E	E	E	E
2	D	D	D	S	S	S	E	E	E	E
3	DU	DU	D	D	D	S	S	S	S	S
4	.	DU	DU	DU	D	D	D	D	D	S

5	.	.	DU	DU	DU	DU	DU	D	D	D
6	.	.	.	DU	DU	DU	DU	DU	DU	D
7	DU	DU	DU	DU	DU	DU
8	DU	DU	DU	DU	DU
E = escalate to the next higher dose level						S = stay at the current dose level				
D = de-escalate to the next lower dose level						DU = de-escalate to the next lower dose level and current dose level will never be used again due to unacceptable toxicity				

Note: For each dose level, a minimum of 3 evaluable subjects will be enrolled and evaluated before a dose escalation/stay/de-escalation decision can be made unless unacceptable toxicity is observed prior to the enrollment of 3 subjects e.g., two subjects experience DLT before the third subject enrolls.

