Number of subjects with DLT	Number of DLT Evaluable Subjects									
	3	4	5	6	7	8	9	10	11	12
0	E	E	E	E	E	E	E	E	E	E
1	S	S	E	E	E	E	E	E	E	E
2	D	D	D	S	S	S	E	E	E	E
3	DU	DU	D	D	D	D	S	S	S	S
4	.	DU	DU	DU	D	D	D	D	D	S
5	.	.	DU	DU	DU	DU	DU	D	D	D
6	.	.	.	DU	DU	DU	DU	DU	DU	D
7	DU	DU	DU	DU	DU	DU
8	DU	DU	DU	DU	DU
E = escalate to the next higher dose level					S = stay at the current dose level					
D = de-escalate to the next lower dose level					DU = de-escalate to the next lower dose level and current dose level will never be used again due to unacceptable toxicity					

Note: For each dose level, a minimum of 3 evaluable subjects will be enrolled and evaluated before a dose escalation/stay/de-escalation decision can be made unless unacceptable toxicity is observed prior to the enrollment of 3 subjects e.g., two subjects experience DLT before the third subject enrolls.

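### Protocol Table 12 prints stay at 3 DLTs in 8 subjects, where the protocol's own rule, its mTPI-2 model and SAP Table 3 all give de-escalate

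*Protocol*

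**What the plan says.** Protocol Section 9.1.1 states the design in full: "The SL-172154 dose escalation will utilize an mTPI-2 design [Guo, 2017] with a target DLT rate of 30% for the MTD". The unit interval "is divided into subintervals with equal length of 0.1 that correspond to different dose escalation decisions". The "subinterval of (0.25, 0.35) is to stay at the current dose", and the "subinterval above 0.35 is to de-escalate to the next lower dose". The prior is Beta(1,1), the subinterval with the highest unit probability mass determines the decision, and a dose is closed as unacceptably toxic (DU) if the probability that its DLT rate exceeds 30% is at least 95%.

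The section then gives threshold rules on the observed rate: escalate below 25%, stay from 25% to 33%, and "Dose de-escalate if the observed DLT rate > 33" per cent.

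The row for 3 DLTs, for n = 3 to 12, differs between the two documents:

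- Protocol Table 12: "3 DU DU D D D S S S S S"
- SAP Table 3 (SAP Section 3.2.1): "3 DU DU D D D D S S S S"

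The leading 3 is the row label. The rows differ only in the sixth entry, n = 8, where the protocol has S and the SAP has D. SAP Section 3.2.1 repeats the same model and the same threshold rules, and SAP Section 11 declares no changes from the protocol's analyses.

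**The concern.** Three of eight is 37.5%, which the protocol's own threshold rule sends down a dose level, yet its table says to stay. The table also disagrees with itself: it prints D at 4 of 11 (36.4%), a lower observed rate, and S at 3 of 8.

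Table 12 is what investigators and the Safety Monitoring Committee will read when they make a dose decision. Anyone following it in this cell would keep enrolling at a dose that the design says to leave, while anyone working from the SAP would step down. DLT-based determination of the MTD is a primary outcome, and nothing in either document acknowledges or resolves the conflict.

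**Working it through.** **Inputs, all from Protocol Section 9.1.1.** Prior Beta(1,1); target 30%; subintervals of length 0.1 built outward from the stay interval (0.25, 0.35); the largest unit mass decides; DU if P(rate > 0.30) ≥ 0.95.

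**Formulas.** With x DLTs in n evaluable subjects the posterior is Beta(1 + x, 1 + n − x). For a subinterval (a, b), the unit mass is [F(b) − F(a)] / (b − a), where F is the posterior distribution function.

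**Reproducing the tables.** This was computed for x = 0 to 8 and n = 3 to 12, which is 75 populated cells. SAP Table 3 reproduces in 75 of 75. Protocol Table 12 reproduces in 74 of 75, and the only mismatch is x = 3, n = 8. The implementation therefore recovers the sponsor's own figures everywhere else.

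**The disputed cell.** For x = 3, n = 8 the posterior is Beta(1 + 3, 1 + 5) = Beta(4, 6).

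| Subinterval | Posterior mass | Unit mass (mass / 0.1) | Decision |
|---|---|---|---|
| (0.35, 0.45) | 0.2475 | 2.475 | D |
| (0.25, 0.35) | 0.2254 | 2.254 | S |
| (0.45, 0.55) | 0.1956 | 1.956 | D |
| (0.15, 0.25) | 0.1318 | 1.318 | E |

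The largest unit mass lies in (0.35, 0.45), so the decision is de-escalate. P(rate > 0.30) = 0.730, below 0.95, so the cell is D and not DU.

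**Threshold rule.** 3/8 = 37.5% > 33%, so D. Taking 33% as one third and DU as a form of de-escalation, the threshold rules agree with Table 12 in every cell except this one.

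**Could another reading produce S?**

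- Handling of the short end intervals (actual length, nominal 0.1, or dropped): D in all three.
- Prior Beta(0.5, 0.5): still D, and four other Table 12 cells no longer match.
- Prior Beta(0.005, 0.005): S at 3 of 8, but nine other cells no longer match.
- Three-interval mTPI: S at 3 of 8 (unit mass 2.254 for stay, 0.937 for de-escalate), but both documents specify mTPI-2.

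**How 8 evaluable subjects can arise.** One path is 1 of 3 (S), then 2 of 6 (S), then a third cohort with one DLT and one non-evaluable subject, which gives 3 of 8. For a true DLT rate p, the chance of reaching the cell on a dose's first pass is:

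- Accrual 3 + 3 + 2: [3p(1−p)²]² × 2p(1−p). At p = 0.3 this is 0.441 × 0.441 × 0.42 = 8%; at 0.4, 0.432 × 0.432 × 0.48 = 9%; at 0.5, 0.375 × 0.375 × 0.5 = 7%.
- Accrual 4 + 4 (1 of 4 is S, then 2 of 4): 4p(1−p)³ × 6p²(1−p)². At p = 0.3 this is 0.4116 × 0.2646 = 11%; at 0.4, 0.3456 × 0.3456 = 12%; at 0.5, 0.25 × 0.375 = 9%.

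These figures apply only if accrual follows the pattern shown.

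**The case against.** The case for treating this as minor has four parts.

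- **Off the nominal path.** With cohorts of exactly three, decisions fall at n = 3, 6, 9 and 12, where Table 12 is correct. This is true, but the protocol makes cohort size approximate, counts only DLT-evaluable subjects (Section 9.2.1) and allows extra subjects (Section 9.1.4). It prints an n = 8 column for that reason.
- **Limited exposure and a close call.** Evaluable subjects are capped at 12 per dose, so at most 12 − 8 = 4 more could follow at that level, and the cells for n = 9 to 12 are right. The unit masses are also close (2.475 against 2.254), and at 3 of 9 the model itself says stay (2.620 against 2.478). This limits the harm, but a close call is still a defined decision.
- **Committee judgement.** The Safety Monitoring Committee meets monthly during escalation and weighs DLT severity and other factors, and the correct text sits beside the table. That may catch the error, but it does not correct the printed instruction.
- **The 33% rule is rounded.** Read literally, 1/3, 2/6, 3/9 and 4/12 (33.3%) also exceed 33%, yet both tables print S there. This part stands: the correction should rest mainly on the model and SAP Table 3. At 37.5% the rounding makes no difference.

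**Conclusion.** The error is real and confined to one cell. At 3 DLTs in 8 evaluable subjects the protocol's stated mTPI-2 model, its threshold rule and SAP Table 3 all give de-escalate, and Table 12 alone says stay. The conclusion rests only on the design as written in Section 9.1.1; no alternative tried yields S without departing from that text or contradicting other cells of the same table.

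The practical reach is modest. The cell matters only if a decision is taken at exactly 8 evaluable subjects, with a first-pass probability of about 7% to 12% under the two accrual patterns and the true rates of 30% to 50% examined. When it does apply, it keeps subjects at a dose with a 0.73 posterior probability of a DLT rate above 30%. A dose-decision table that is wrong in the unsafe direction should be corrected however rarely the cell is used.

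**What to change.** Change the 3-of-8 entry in Protocol Table 12 from S to D. Table 12 then matches the stated model in 75 of 75 cells and is identical to SAP Table 3, which needs no change.

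In the same edit, word the thresholds in both documents in terms of one third, so that 1/3, 2/6, 3/9 and 4/12 fall clearly under stay. Confirm from the dose-decision records whether any decision was taken at 3 of 8 and, if so, document how it was handled. The table still matters after the planned levels are complete, because both documents allow further doses or schedules to be explored.

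The cost is one table cell and a small wording change, by amendment or by clarification memo, a route the sponsor has already used in this study. Sample size, analyses and data collection are unaffected.

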9.1.2 Dose Expansion

For the SL-172154 + PLD dose expansion cohort, the goal is to enroll approximately 20 subjects treated at the potential RP2D in either dose expansion or dose escalation. The sample size of 20 is primarily chosen to obtain a preliminary assessment of the antitumor activity with a certain degree of precision. [Table 13](#) provides the 90% confidence interval (CI) based on exact probability method for a range of possible responses out of 20 subjects. Approximately 14 of these subjects at the potential RP2D will be enrolled in the dose expansion cohort.

Table 13 Response Rate 90% CI Out of 20 Subjects

# Responses/20 Subjects	Response Rate	90% CI
2	10%	1.8%, 28.3%
4	20%	7.1%, 40.1%
6	30%	14.0%, 50.8%
8	40%	21.7%, 60.6%
10	50%	30.2%, 69.8%
12	60%	39.4%, 78.3%
14	70%	49.2%, 86.0%
16	80%	59.9%, 92.9%
18	90%	71.7%, 98.2%

For the SL-172154 + MIRV dose expansion cohort, the goal is to enroll approximately 20 subjects treated at the potential RP2D for each of the following three tumor FR α expression subgroups in either dose expansion or dose escalation: high (PS2+ \geq 75%), medium (PS2+ \geq 50% and < 75%), and low (PS2+ \geq 25% and < 50%). The sample size of 20 is primarily chosen to obtain a preliminary assessment of the antitumor activity with a certain degree of precision ([Table 13](#)). Approximately 64 subjects treated at the potential RP2D will be enrolled in the dose expansion cohort.

9.1.3 Safety Monitoring During Dose Expansion

Each dose expansion cohort will allow further characterization of the safety profile of SL-172154 in combination with either PLD or MIRV, with particular emphasis on toxicities

leading to discontinuation of SL-172154 and the combination agents. Continuous toxicity monitoring based on Pocock-type stopping boundary [Ivanova, 2005] will be used within each dose expansion cohort. Accrual will be temporarily stopped if an excessive number of subjects discontinue SL-172154 and a combination agent due to toxicities.

9.1.3.1 Safety Monitoring in the SL-172154 + PLD Dose Expansion Cohort

In the JAVELIN Ovarian 200 study, the discontinuation rate in the PLD monotherapy group owing to AEs was 11% and treatment-related AEs leading to treatment discontinuation was 7% [Pujade-Lauraine, 2021], thus a 20% rate of AE leading to treatment discontinuation regardless of causality is selected as the Pocock-type stopping boundary for the SL-172154 + PLD dose expansion cohort. Enrollment to the SL-172154 + PLD dose expansion cohort will be temporarily stopped if an excessive number of subjects experience AEs leading to treatment discontinuation; that is, if the number of subjects with AEs leading to treatment discontinuation is equal to or more than b_n out of n subjects as described in the table below. The sequential stopping boundaries are selected to have at least 70% probability to temporarily stop when the underlying true rate of subjects with AEs leading to treatment discontinuation is 10% higher than 20%.

Number of subjects, n	1	2	3	4	5	6	7	8	9	10	11	12	13	14	15	16	17	18	19	20
Boundary, b_n	-	2	3	3	3	3	4	4	4	4	4	4	5	5	5	5	5	6	6	6

9.1.3.2 Safety Monitoring in the SL-172154 + MIRV Dose Expansion Cohort

In the IMGN853-0401 study, 15% of the subjects at 6.0 mg/kg MIRV monotherapy discontinued treatment due to AEs (MIRV IB), thus a 20% rate of AE leading to treatment discontinuation regardless of causality is selected as the Pocock-type stopping boundary for the SL-172154 + MIRV dose expansion cohort. Enrollment to the SL-172154 + MIRV dose expansion cohort will be temporarily stopped if an excessive number of subjects experience AEs leading to treatment discontinuation; that is, if the number of subjects with AEs leading to treatment discontinuation is equal to or more than b_n out of n subjects as described in the table below. The sequential stopping boundaries are selected to have at least 82% probability to stop when the true underlying rate of subjects with AEs leading to treatment discontinuation is 10% higher than 20%.

Number of subjects, n	1	2	3	4	5	6	7	8	9	10	11	12	13	14	15	16	17
Boundary, b_n	-	-	3	4	4	4	5	5	5	5	6	6	6	6	7	7	7
Number of subjects, n	18	19	20	21	22	23	24	25	26	27	28	29	30	31	32	33	34
Boundary, b_n	7	8	8	8	8	9	9	9	9	10	10	10	10	11	11	11	11
Number of subjects, n	35	36	37	38	39	40	41	42	43	44	45	46	47	48	49	50	51
Boundary, b_n	11	12	12	12	12	12	13	13	13	13	14	14	14	14	15	15	15
Number of subjects, n	52	53	54	55	56	57	58	59	60	61	62	63	64	65			

Boundary, b_n	15	15	15	16	16	16	16	17	17	17	17	18			
-----------------	----	----	----	----	----	----	----	----	----	----	----	----	--	--	--

9.1.4 Sample Size Determination

The planned sample size is approximately 102 subjects, depending on the number of dose levels evaluated in dose escalation for each of the combinations. Approximately 24 subjects will be enrolled in dose escalation cohorts (12 subjects in PLD cohorts and 12 subjects in MIRV cohorts) and approximately 78 subjects will be enrolled in a dose expansion cohort (an additional 14 subjects at the selected dose in PLD cohort and an additional 64 subjects at the selected dose in MIRV cohort).

All subjects with tumors that are FR α -positive (PS2+ \geq 25%) enrolled in the MIRV combination cohort will be retrospectively binned in expression subgroups (high, medium, low) for study analysis. The goal is to enroll approximately 20 subjects at the potential RP2D in either dose expansion or dose escalation for each of the following three tumor FR α expression subgroups: high (PS2+ \geq 75%), medium (PS2+ \geq 50% and $<$ 75%), and low (PS2+ \geq 25% and $<$ 50%). This estimation is based on the anticipated frequency of subjects with high grade serous ovarian cancer who fall into each of these FR α expression subgroups. If this distribution is not achieved in any subgroup, approximately 10 additional subjects may be enrolled in this dose expansion cohort in order to achieve it.

NOTE: The planned sample sizes may be revised if additional dose levels are evaluated or if more subjects (i.e., subjects available for dosing beyond the number required in a cohort) are enrolled than anticipated. The actual number of subjects to be enrolled for each combination dose escalation will depend upon the number of dose levels evaluated and the number of DLT observed for each dose level and related dose escalation/stay/de-escalation decisions. The Sponsor, in consultation with the SMC, may also elect to add subjects to the dose escalation cohorts if additional data is needed to select the dose level for the dose expansion cohort.

